6.4.5 Discharge Evaluation

Discharge evaluations will occur at hospital discharge or between 24 hours and 14 days postoperatively. Discharge evaluations consist of:

- Clinical signs or symptoms of bleeding;
- Reoperation;
- Use of any blood modifiers, insulin, or blood sugar lowering medications or reversal drugs;
- Total hospitalization time;
- Incidence of any complications/AEs;
- Drainage volume, as applicable;
- Time of drain volume measurement, as applicable;
- Time of drainage removal, as applicable; and
- Deep Vein Thrombosis (DVT) prophylaxis methods and duration.

The Discharge eCRF must be completed at discharge. The Blood Modifiers/Insulin or Blood Sugar Lowering Medications eCRF, Adverse Event eCRF, and Reoperation eCRF should also be completed as applicable.

6.4.6 Follow-up Evaluation

A follow-up evaluation will be performed at 6 weeks postoperatively (between 28-56 days). Unscheduled follow up evaluations are at the discretion of the investigator and may occur at any time prior to the 6 week follow up evaluation.

The Follow-Up eCRF must be completed for the follow-up evaluation. The Blood Modifiers/Insulin or Blood Sugar Lowering Medications eCRF, Adverse Event eCRF, and Reoperation eCRF should also be completed as applicable. The completion/discontinuation eCRF will be completed for each subject at the completion of the 6 week follow-up visit or whenever applicable (i.e., upon subject death or subject withdrawal).

6.4.6.1 Six-week Postoperative Follow-Up Evaluation

- Clinical signs or symptoms of bleeding;
- Clinical signs or symptoms of embolism or thrombosis
- Reoperation and Re-Hospitalizations;
- Use of any blood modifiers, insulin, or blood sugar lowering medications or reversal drugs;
- Thromboembolism Assessment;
- DVT prophylaxis methods and duration; and
- Incidence of any complications/AEs.

6.4.6.2 24 Month Postoperative Follow-Up Evaluation (*for oncologic subjects only*)

- Assessment of Overall Survival: At 24 months, overall survival will be conducted. This may be completed by a medical records review, confirmation of an obituary, or other contact (phone call, email, letter, etc.). If there is no response after 3 documented attempts (one of which must be a certified letter), the subject will be considered lost to follow up.

6.4.7 *Evaluation Schedule*

Table 3 summarizes the acceptable visit windows for each evaluation time point.

Table 3. Visit Windows for Evaluations

Visit Type	Timing
Preoperative	Within 1 month (30days) before operative visit
Operative	Day 0
Postoperative	Within 24 hours postoperatively
Follow-Up: Discharge	Within 24 hours of hospital discharge or between 24 hours and 14 days postoperatively
Follow-Up: 6 Week	28-56 days postoperatively
Follow-Up: 24 Months*	23-25 months (700-760 days) postoperatively

*for oncologic subjects only

Table 4 summarizes the eCRFs that need to be completed at each time point.

Table 4. Completion of eCRFs

eCRF	Screening	Preoperative	Operative	Postoperative	Discharge	Follow-Up Visit(s)	Discontinuation
1: Subject Screening Form	X						
2: Preoperative Form		X					
3: Operative Form			X				
4: Postoperative Form				X			
5: Discharge Form					X		
6: Follow-Up Form						X	
7: Blood Modifiers Form	Where Applicable						
8: Laboratory Form		X		X			
9: Reoperation Form	Where Applicable						
10: Adverse Event Form	Where Applicable						
11: Discontinuation Form	Where Applicable						
12: Protocol Deviation Form	Where Applicable						
13: Equipment Calibration Form			X				

6.5 Monitoring Plan

Monitoring of the clinical trial will be a continuous, interactive process overseen by the Sponsor or Sponsor representative to ensure that high-quality data are obtained. Appropriately trained personnel designated by the Sponsor or Sponsor representative will monitor all subjects at the investigational site. Monitoring will be conducted according to 21 CFR Part 812, 21 CFR Part 50, ICH E6, as recognized by FDA, and by the Sponsor or Sponsor representative's applicable standard operating procedures (SOPs) and under the guidelines specified in the Monitoring Plan. In addition, the Sponsor or Sponsor representative may conduct an internal audit of the trial for quality assurance. Other inspections by regulatory authorities may include on-site inspections and source data verification.

6.5.1 Pre-Trial/Qualification Visit

The Sponsor or Sponsor representative will conduct a pre-trial (or qualification) visit to review the clinical protocol and regulatory requirements with the Investigator and trial personnel to assure the following:

- The site understands the investigational use of the device;
- The site understands the protocol;
- The site understands and accepts the obligation to conduct the clinical investigation in compliance with the protocol, the Sponsor and/or Sponsor representative policies and procedures, applicable laws, regulations and good clinical practices;
- The site understands and accepts the obligation to obtain informed consent in accordance with applicable regulations;
- The site understands and accepts the obligation to obtain IRB approval before the clinical investigation is initiated, ensures continuing review of the trial by the IRB, and keeps the Sponsor or Sponsor representative informed of the IRB approval and actions concerning the trial;
- The site has access to an adequate number of eligible subjects to participate in the trial;
- The site has adequate facilities and resources to conduct the trial; and
- The site has sufficient time to carry out the responsibilities of the trial.

A report of this visit will be completed. The site will be notified of any concerns or required follow-up items from the pre-trial visit. Resolution of these will be documented.

A Study Initiation Visit will be conducted prior to the enrollment of any subjects.

6.5.2 Periodic Monitoring Visits

Monitoring visits during the trial are necessary to assess the Investigator's adherence to the protocol, agreement, and applicable regulations. Monitoring will occur at a mutually agreeable time. One hundred percent (100%) of the data will be monitored for this trial.

6.5.3 Closeout Visits

A closeout visit will be conducted once a site is no longer enrolling and patient follow-up is complete, the trial is completed, or site activities have been terminated by the Sponsor and/or applicable regulatory agency. There may be instances where a phone call close-out may occur (e.g., for a site that did not enroll any subjects). During the study closeout, the monitor will address administrative and regulatory record requirements.

6.5.5 Source Document Verification

To ensure accurate and complete data are collected, 100% source document verification will be performed on all subjects at each site. This verification requires all data to be reviewed in the source documents and in the eCRF.

Only site staff listed on the Delegation of Responsibilities Log is authorized to enter data or make corrections to eCRFs.

6.5.6 Protocol Deviations/Violations

The Investigator will not deviate from the protocol without the prior written approval of the Sponsor except in unforeseen, isolated instances where minor changes are made that will not increase the subject's risk or affect the validity of the investigation or in cases to eliminate immediate hazards to a subject. Prior approval for protocol deviations will not be required in such cases; however, protocol deviations will be documented on the applicable Protocol Deviation Log eCRF provided by the Sponsor or Sponsor Representative.

For the purposes of this investigation, protocol violations are defined as entry of a subject into the investigation against inclusion/exclusion criteria without prior Sponsor approval. Deviations are defined as less severe protocol non-compliance such as visits occurring outside the visit time window. Sites should be instructed to follow their local IRB rules and any other applicable requirements for reporting protocol deviations/violations.

6.6 Statistical Considerations

Sections below provide detail on statistical aspects of the study design. Additional detail is provided in the Statistical Analysis Plan for the study.

6.6.1 Trial Objectives and Endpoints

The primary objective of this clinical investigation is to demonstrate non-inferiority in the achievement of hemostasis of the treated bleeding site at 7 minutes in subjects receiving PerClot compared to those receiving a control hemostatic device. The primary endpoint is the proportion of subjects achieving hemostasis of the treated lesion at 7 minutes in each treatment group.

The secondary objective of this investigation is to compare the achievement of hemostasis of the treated bleeding site evaluated at 5 minutes for subjects receiving PerClot compared to those receiving a control hemostatic device. The secondary endpoint is the proportion of subjects achieving hemostasis of the treated bleeding site at 5 minutes in each treatment group.

6.6.2 Primary Efficacy Hypothesis

The primary efficacy hypothesis for this clinical investigation is that the proportion of subjects achieving hemostasis of the treated bleeding site at 7 minutes in the overall PerClot group is non-inferior to the proportion of subjects achieving hemostasis at 7 minutes in the overall control group.

$$H_0: P_{\text{PerClot}} < P_{\text{Control}} - \delta$$
$$H_a: P_{\text{PerClot}} \geq P_{\text{Control}} - \delta$$

where P_{PerClot} is the proportion of PerClot subjects achieving hemostasis at 7 minutes, P_{Control} is the proportion of control subjects achieving hemostasis of the treated bleeding site at 7 minutes, and δ is the non-inferiority margin, with $\delta = 0.10$.

The primary efficacy endpoint measure will also be reported by therapeutic area (subgroup): open elective cardiac, general, or urological surgical procedures. The proportion of PerClot and control subjects achieving hemostasis at 7 minutes will be reported, along with the absolute difference between the groups. A poolability analysis will also be performed on the therapeutic area subgroups. See Section 6.6.12. There are no labeling claims being sought out for this subgroup analysis.

Additionally, the number of subjects in whom hemostasis is achieved at 7 minutes, but have a re-bleed during the 5 minute observation period following the 7 minute assessment will be summarized. A sensitivity analysis of the endpoint will be conducted where all subjects that achieved hemostasis at 7 minutes, but did not maintain it for the 5 minutes following the assessment or any time after the observation period, will be counted as ‘failures’ in the analysis.

For subgroups, with an overall enrollment of 324 subjects in the study in the treatment and control cohorts, it is expected that there will be data on approximately 108 subjects in each subgroup. At a minimum, the study will enroll 50 subjects within a specific therapeutic area subgroup. At a maximum there will be 224 subjects in a single subgroup. A minimum of 50 subjects in each subgroup would lead to approximately 25 treatment subjects per subgroup. For a success rate of 92% (23/25), the distance from the observed rate of 92% to the lower bound of the two-sided 95% confidence interval is 18.0%. This planned minimum subgroup size would provide a reasonable degree of statistical precision for estimation of the treatment performance within subgroups.

6.6.3 Secondary Efficacy Hypothesis

The secondary efficacy endpoint will be evaluated at 5 minutes in a manner similar to the primary efficacy analysis. The secondary hypothesis for this clinical investigation is that the proportion of subjects achieving hemostasis of the treated lesion at 5 minutes in the overall PerClot group is non-inferior to the proportion of subjects achieving hemostasis of the treated bleeding site at each evaluation time point in the overall control group.

$$H_0: P_{t,PerClot} < P_{t,Control} - \delta$$
$$H_a: P_{t,PerClot} \geq P_{t,Control} - \delta$$

where $P_{t,PerClot}$ is the proportion of PerClot subjects achieving hemostasis of the treated bleeding site at time point t , $P_{t,Control}$ is the proportion of control subjects achieving hemostasis of the treated bleeding site at time point t , and δ is the non-inferiority margin, with $\delta = 0.10$.

The secondary efficacy endpoint measure will also be reported by therapeutic area (subgroup): open elective cardiac, general, or urological surgical procedures. The proportion of PerClot and control subjects achieving hemostasis at 5 minutes will be reported, along with the absolute difference between the groups. These analyses are descriptive in nature, and as such there are no formal hypothesis tests. There are no labeling claims being sought out for this subgroup analysis.

Additionally, the number of subjects in whom hemostasis is achieved at 5 minutes, but has a re-bleed after the 5 minute assessment will be summarized. A sensitivity analysis of the endpoint will be conducted where all subjects that achieved hemostasis at 5 minutes, but did not maintain it after the assessment will be counted as ‘failures’ in the analysis.

6.6.4 Safety Analysis

Safety data will be summarized by incidence of each adverse event type along with 95% exact confidence intervals. Adverse event rates will be reported as the proportion of subjects who experience an event and the total number of each event type occurring. Adverse events will be summarized by relatedness, seriousness, and severity. The comparison of the safety between treatment arms will be based on Fisher’s exact tests for the proportion of subjects with serious device-related adverse events, unanticipated adverse device effects, and frequent adverse events ($\geq 5\%$ overall incidence) in the two treatment groups.

Additionally, supportive descriptive analyses will be performed on adverse event data within each therapeutic area: open elective cardiac, general, or urological surgical procedures.

The other following safety endpoints will also be summarized using descriptive statistics:

- Total operative time;
- Hemostasis at 5 and 7 minutes;
- Hemostasis maintenance;
- Total intraoperative estimated blood loss;
- Alternative means required to achieve hemostasis (where applicable);
- Units of blood transfused intraoperatively and postoperatively (where applicable);
- Incidence of reoperation;
- Total hospitalization time;
- Incidence of procedure complications;
- Incidence of adverse events through final follow-up, including, but not limited to:
 - Adhesions or fibrosis;
 - Anaphylaxis;
 - Blockage of the bladder or ureteral lumen;

- Blockage of the bypass system;
- Cancer recurrence and/or progression;
- Compromised attachment of prosthetic devices to bone or tissue;
- Death;
- Embolism;
- Failure of deep or superficial wound healing;
- Failure to obtain hemostasis;
- Fever;
- Hemorrhage;
- Infection;
- Peri-operative hyperglycemia;
- Exacerbation of surgical procedure-associated adverse events;
- Swelling and compression of pressure-sensitive tissues and structures;
- Thromboembolism;
- Thrombosis; and
- Toxicity.

6.6.5 *Sample Size Justification*

The sample size was calculated based on the following assumptions:

- One-sided $\alpha = 0.025$;
- Minimum 80% power;
- Non-inferiority margin $\delta = 0.10$;
- Expected 7 minute hemostatic success rate in the PerClot group is 90%;
- Expected 7 minute hemostatic success rate in the control group is 90%; and
- Randomization allocation of 1:1.

A sample size of 154 subjects in each group will provide $>$ approximately 80% power to reject the hypothesis of the inferiority of PerClot to the control by a 10% margin, using a one-sided 97.5% confidence interval. As the primary endpoint data is collected intraoperatively, no adjustment is made for attrition; however, the sample size was increased to account for the possibility of up to 5% loss within either group due to technical failures (i.e., contraindications, misdiagnosis, or intraoperative death prior to treatment, etc.), or subjects not treated according to randomization assignment, resulting in a sample size of 162 per arm to ensure $>$ 80% power in the overall sample including all three therapeutic areas. Thus, a total of 324 subjects will be enrolled across the three therapeutic areas. It is expected that there will be approximately equal numbers randomized within each of the three therapeutic areas, with an approximate 108 subjects in each therapeutic cohort.

A non-inferiority margin of 10% is consistent with the margins used in other controlled clinical trials involving hemostatic agents.^{24, 25} A non-inferiority margin $\delta = 0.10$ was chosen for this study because excluding a 10% difference between the treatments would be supportive of non-inferior performance of PerClot compared to the control.

6.6.6 *Blinded Sample Size Re-estimation*

In order to protect against lower than planned power due to misspecification of the assumed success rates, blinded sample size re-estimation will be performed.²⁶ The initial sample size

calculation will be repeated based on the observed pooled efficacy rate (i.e. the proportion of all subjects, regardless of randomization assignment, with 7 minute hemostatic success) rather than the initially assumed rate of 90%.

The re-estimation will be performed using the efficacy results of the first 20% and 50% of the minimum planned enrollment of 324(i.e. 64 and 162 subjects) pooled across randomized arm. The re-estimated sample size after 20% enrollment will provide an initial re-calibration of the sample size. The re-estimated sample size after 50% enrollment will determine the final sample size, which may be lower or higher than the re-estimated sample size after 20% enrollment.

The sample size calculation will result in an increase in sample size if the observed efficacy rate is less than 90%. The loss rate at the interim analysis will be estimated and provided to the DSMB. In making a sample size recommendation, the DSMB may adjust the re-estimated sample size by up to 5% for the loss rate. The minimum sample size for the trial, regardless of the observed efficacy and loss rates, is the initially planned sample size of 324. A maximum sample size is set at 536 (510 with a 5% loss adjustment) for any observed efficacy rate $\leq 80\%$. The table below provides examples of the revised sample size before adjusting for loss based on hypothetical results.

Table 5: Re-estimated sample size based on blinded efficacy rate before adjusting for loss

Blinded Efficacy Rate	Re-estimated Sample Size
90%	308
89%	332
88%	352
87%	374
86%	394
85%	414
84%	434
83%	454
82%	474
81%	492
80%	510

Because the sample size re-estimation is blinded and based only on a nuisance parameter, there is no impact on the Type I error rate. Larger sample sizes are required due solely to greater variability in the binomial outcome when the equal PerClot and control efficacy rates are closer to 50%, at which point variability is at a maximum.

If the observed efficacy rate is $\leq 60\%$ when the blinded sample size re-estimation is performed at 20% of enrollments or $\leq 64\%$ when the blinded sample size re-estimation is performed at 50% of enrollments, the DSMB will evaluate the overall study data and make a recommendation regarding whether to stop the study prematurely due to an unacceptable efficacy rate. The boundaries of 60% and 64% were selected based on those observed rates have $<5\%$ chance of being observed if the population efficacy rate is 70% or higher.

6.6.7 Trial Success Criteria

Trial success will be the rejection of the primary efficacy null hypothesis, with the upper bound of the 97.5% one-sided confidence interval for the difference in proportions of subjects achieving hemostasis at 7 minutes between overall treatment groups ($P_{Control} - P_{PerClot}$) being less than 0.10, in the As Treated population.

6.6.8 Randomization and Blinding

The randomization schedule is a set of lists of sequential randomization assignments. The schedule will be stratified by site, therapeutic area and bleeding severity score. Stratifying the randomization is performed in order to help ensure that randomization is balanced between the two arms within each stratum. Therefore each site will have its own set of randomization envelopes for each bleeding severity score and therapeutic area that are independent of other sites. In creating the randomization schedule, the list of randomization assignments is composed of a series of permuted random blocks with each block consisting of two or four randomization assignments. The size of each block in the sequence is selected at random. The random permuted block method ensures that as subjects are randomized, the randomization returns to balance once each sequential block is filled, thus ensuring that the size of any imbalance is limited throughout the accrual of subjects into the study. Subjects will be randomized on a 1:1 allocation to either PerClot or the control group. A subject may agree to participate and sign the ICF, but ultimately not be enrolled due to failure to meet the intraoperative eligibility criteria. Only subjects meeting the intraoperative eligibility criteria will be randomized and enrolled.

This will be a single blinded trial. The subjects will be blinded as to the hemostatic treatment received. Unblinding will be permitted after a subject has completed his or her 6 week follow-up visit evaluation.

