After confirmation of the intraoperative eligibility criteria, the subject will be randomized to receive an adjunct application of PerClot or the control device. The randomization schedule will be stratified by site, therapeutic area and bleeding severity score. Subjects will be randomized on a 1:1 allocation to either PerClot or the control group via envelope randomization. The Randomized Study Device (RSD) will be provided in a manner which will maintain product sterility.

There may be cases in which a subject is randomized but expires before the prescribed hemostatic agent can be applied. In such cases, this will be documented on the screening and enrollment log. Also see Section 6.1.2.

After randomization, the following data will also be collected and documented on the Operative eCRF:

- Identifier number;
- Surgeon;

- Technical failures;
- Diastolic and systolic blood pressure;
- Pulse;
- Core body temperature;
- Use of any blood modifiers, insulin or blood sugar lowering medications; and
- Blood glucose measurement.

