Appendix N: Operative Steps

Operative Steps

	Investigator	Coordinator/Surgical Associate
1		
a. Assure all necessary equipment are present and ready for use, including:
 
  Writing utensil with indelible ink;  Calibrated mass balance (readability and repeatability in milligrams, 0.001 g);  Timing device (precision in seconds);  Millimeter incremented tool;  Study Devices (2 packaged 5g bellows of PerClot and 2 packaged 5g bellows of Arista)  Calculator or device with calculator function;  Sterile bowl;  Paper copy of Operative Worksheets;  2 packages Covidien™ Vistec™ X-ray Detectable Sponges, 16-Ply, 4" x 4" (hereinafter referred to as gauze)  1 liter of warm saline; and  Envelopes for randomization. 
b. Tare calibrated scale.
 
c. Pre-weigh packaged, sterile gauze in grams to 3 decimal places (0.001 g increments) and record.
 
d. In a manner that will not compromise sterility, introduce pre-weighed and non-weighed sterile gauze to the sterile field until ready for use.
 
e. Visually inspect the sealed packages of devices. If either package has been previously opened or damaged, discard and replace with a new package.
 
f. Pre-weigh packaged Study Devices in grams to 3 decimal places (0.0001 g increments) and record.

2	
a. Perform conventional methods for hemostasis, including but not limited to, pressure and ligature.
 
b. Blot bleeding site with clean non-weighed gauze and gentle pressure to remove blood and any other fluid from the study site.
 
c. Ligate any remaining vessels or suture holes >= 2 mm diameter.
	

	Investigator	Coordinator/Surgical Associate
3	
a. Inspect the bleeding site. Determine whether additional hemostatic measures need to be performed by application of a topical hemostat agent.
	

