*For oncology subjects only.

3 Randomization and Blinding

The randomization schedule will be stratified by site, therapeutic area, and bleeding severity score, and will be generated using random permuted blocks of size two and four. Subjects will be randomized on a 1:1 allocation to either PerClot or the control group. A subject may agree to participate and sign the ICF, but ultimately not be enrolled due to failure to meet the intraoperative eligibility criteria. Only subjects meeting the intraoperative eligibility criteria will be randomized and enrolled.

This will be a single-blinded trial. The subjects will be blinded as to the hemostatic treatment received. Unblinding will be permitted after a subject has completed his or her 6 week follow-up visit evaluations.

4 Statistical Methods

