Success of the primary and secondary endpoints is determined by the treating physician's assessment. A supplementary secondary analysis of hemostasis endpoints will be performed based on the overall majority rule CEC assessment of hemostasis. The use of the CEC adjudications for analysis applies to all randomizations under protocol version 11 amendment 4 through version 11 amendment 7, as video capture was added to the protocol under version 11 amendment 4 and version 11 amendment 7 was the last amendment to require video capture. This analysis, which is based on CEC assessment of hemostasis rather than treating physician assessment, will exclude subjects randomized under a version of the protocol that does not require capture of video.

The CEC members assess a video of the bleeding region captured during the procedure. If the first two readers to assess a video agree about the outcome, a third reader is not required. A majority of two out of three members in agreement with each other is required to determine the overall CEC assessment. The table below indicates how the reader assessments are used to determine the overall CEC assessment of 7 and 5 minute hemostasis by a majority vote.

Table 4: Clinical Evaluation Committee Individual Assessments and Overall Endpoint Outcome

Clinical Evaluation Committee Individual Assessments			Overall CEC Outcome
Hemostasis	Hemostasis	3rd reader not required	Hemostasis
No Hemostasis	No Hemostasis	3rd reader not required	No Hemostasis

Not Evaluable	Not Evaluable	3rd reader not required	Indeterminate/missing
Hemostasis	No Hemostasis	Hemostasis	Hemostasis
Hemostasis	Not Evaluable	Hemostasis	Hemostasis
Hemostasis	No Hemostasis	No Hemostasis	No Hemostasis
No Hemostasis	Not Evaluable	No Hemostasis	No Hemostasis
Hemostasis	No Hemostasis	Not Evaluable	Indeterminate/missing
Hemostasis	Not Evaluable	Not Evaluable	Indeterminate/missing
No Hemostasis	Not Evaluable	Not Evaluable	Indeterminate/missing

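### Disclosed blocks of 2 and 4 in site-held envelope lists let an unblinded surgeon guess the next arm 65–71% of the time; hiding the sizes and dropping blocks of 2 is a cheap, partial remedy

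*Protocol*

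**What the plan says.** Protocol 6.6.8 describes the schedule as a series of "permuted random blocks with each block consisting of two or four randomization assignments" and adds that "The size of each block in the sequence is selected at random". SAP section 3 says the schedule "will be generated using random permuted blocks of size two and four". On structure, Protocol 6.6.8 states: "The schedule will be stratified by site, therapeutic area and bleeding severity score", so that "each site will have its own set of randomization envelopes for each bleeding severity score and therapeutic area". Protocol 6.4.3.3 confirms the mechanism: "Subjects will be randomized on a 1:1 allocation to either PerClot or the control group via envelope randomization". Appendix N step 1 lists "Envelopes for randomization" among the items to have ready for the operation.

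Only subjects are blinded (Protocol 6.6.8). The surgeon applies the device under device-specific steps (Appendix N) and judges hemostasis (Protocol 6.4.3.5). SAP 4.4.2 makes that judgement decisive: "Success of the primary and secondary endpoints is determined by the treating physician's assessment". The committee reading of videos is supplementary.

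Before the envelope is opened, the surgeon carries out conventional hemostasis and decides whether a topical agent is needed (Appendix N steps 2 and 3). Any bleeding site on the relevant surface may be put forward (Protocol 6.4.3.1), and the resected surface may be larger than the area treated (note in 6.4.3.4).

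**The concern.** With short blocks and a list that one site team can follow, earlier assignments carry information about the next one. A surgeon who expects a given arm can, knowingly or not, put forward an easier or harder bleed, or do more or less conventional hemostasis first. This is selection bias acting before allocation. It can move the difference in success rates in either direction, and so can produce or hide non-inferiority against a 10-point margin. Trial success rests on one binary endpoint, and no planned analysis is aimed at this mechanism.

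**Working it through.** **Inputs.** Block sizes 2 and 4, size chosen at random (Protocol 6.6.8). The selection probabilities are not given, so 50:50 is assumed, with 1:2 to 2:1 as the range. At most 25 sites, 13–40 subjects per site, 324 subjects (Protocol 6.3). Three therapeutic areas. Two eligible severity scores, 1 and 2 (Protocol 6.3.2). Margin 0.10 and 154 evaluable subjects per arm (SAP 4.2.1.1). The documents give no figure for predictability. The sample-size figure reproduces: a Farrington–Manning score test at 90% versus 90% with 154 per arm gives power 0.79885, as in SAP Appendix A.

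**Strata.** The ceiling is 25 × 3 × 2 = 150 lists, or 324/150 = 2.16 subjects per list. If every site works in one area only, there are 25 × 2 = 50 lists, or 324/50 = 6.5 per list.

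**Guessing by position, blocks 2/4.** The first assignment is 50%. The second is 0.5 × 1 + 0.5 × 2/3 = 0.833. Enumerating all sequences gives 58.3% for the third and 91.7% for the fourth; later positions alternate between about 54–56% and 87.5–90%.

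**Guessing over the trial.** Averaging over equally likely strata gives 65% (150 strata), 70% (50) and 71% (16–25). Unevenly filled strata give 66.7% (150) and 70.1% (50). Certain assignments run from 5% (150 strata) to 10% (16–25). Block-size odds from 1:2 to 2:1 give 64–72% correct and 3–13% certain.

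**With blocks 4/6.** The second subject is guessed correctly 0.5 × 2/3 + 0.5 × 3/5 = 0.633 of the time. Over the trial the rate is about 60–68%; with uneven strata it is 62.1% (150) and 66.3% (50).

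**Bias, as an illustration.** Suppose a guess shifts the success chance of the enrolled bleed by e in the favoured direction, and guesses are correct with probability g. Each arm's rate moves by e(2g − 1), in opposite directions, so bias = 2e(2g − 1). The size of e is an assumption; the documents give nothing on it. At g = 0.667, e of 1 to 5 points gives 0.7 to 3.3 points. For e = 5 points:

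| Strata (uneven) | Blocks 2/4 | Blocks 4/6 |
|---|---|---|
| 150 | 0.10 × (2 × 0.667 − 1) = 3.3 points | 0.10 × (2 × 0.621 − 1) = 2.4 points |
| 50 | 0.10 × (2 × 0.701 − 1) = 4.0 points | 0.10 × (2 × 0.663 − 1) = 3.3 points |

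With 154 per arm and true rates of 80% versus 90%, a bias of 4.0 points towards PerClot would raise one-sided type I error from 2.5% to about 16%. A bias of 3.2 points would raise it to about 12%.

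**Cost in balance.** The SD of the overall arm difference rises from 8.9 to 10.3 (150 uneven strata) or from 5.9 to 7.2 (50). The extra information loss is the change in (imbalance/324)², for example (10.3² − 8.9²)/324² = 26.9/104,976 = 0.03%. Across the ways of filling strata that were tried, the SD rises by about 1–2.5 subjects and the loss is about 0.06% or less.

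**The case against.** The other side has real force, and most of it stands as a limit on size.

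- **The protocol already polices selection.** Section 6.1.2 requires the reason to be logged for any intraoperatively eligible subject not enrolled; the log is monitored, and a site introducing bias may be retrained or suspended. Section 6.4.3.2 enrols on a weighed-gauze flux. This covers declining a subject. It does not cover choice among bleeding sites, because sites passed over are not logged. Score 1 alone spans a 0.0056/0.000040 = 140-fold range of flux within one stratum.
- **The list is not yet known when the site is chosen.** The severity score follows from the flux, which is measured afterwards (Appendix N steps 4–8). If severity is judged correctly by eye 70% of the time (an assumption) and a wrong list gives a coin-flip, 66.7% becomes 0.7 × 0.667 + 0.3 × 0.5 = 61.7%.
- **Disclosure does not drive the guess rate.** Someone who ignores block sizes and always guesses the arm used less so far in the stratum scores the same. Withholding the sizes removes knowledge of which assignments are certain. The lower guess rate comes from dropping blocks of 2.
- **Random block size is already a safeguard**, and the fix leaves much of the illustrative bias in place. Both are correct.

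A reader might infer that two-thirds of assignments are known in advance. They are not: 65–71% is a correct-guess rate with 50% due to chance. A reader might also infer that many small strata make matters worse. They make guessing slightly harder (65% at 150 strata, 71% at 16–25), because more subjects are first on a list. Nor do the documents show that one surgeon sees every earlier assignment; sub-investigators may administer the device (Appendix H).

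**Conclusion.** The concern holds as a moderate, avoidable weakness in allocation concealment. The drivers are short blocks and site-level lists, not the number of strata. Correct guessing of about 65–71% is an upper value: it assumes a 50:50 block mix, a guesser who has followed the list, and a severity list known in advance. The bias figures also assume that every subject at every site is steered in the same direction, so they illustrate scale and are not estimates. The documents do not support a reading that steering has occurred or that the result is invalid. Bias from scoring by an unblinded surgeon is a separate matter that exists at any block size. What the documents do support is that the risk can be partly reduced at almost no cost.

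**What to change.** In Protocol 6.6.8, replace the block-size wording with a statement that block sizes vary at random and are recorded only in a restricted randomization specification. Remove the sizes from SAP section 3. For envelope lists not yet issued, drop blocks of 2 (for example, use 4 and 6). The new sizes matter because current investigators have already been able to read the old ones, and unissued lists may be needed if re-estimation raises the sample towards 536.

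The cost is a text edit in two documents, regeneration of unissued lists, and the small loss of balance shown above. Eligibility, treatment, alpha and sample size are unchanged. Envelopes already issued stay as they are. The gain is partial: second-subject guessing falls from 83% to 63% and overall guessing to about 60–68%.
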